7.5.4. PGI-C daily impacts scale responses

• Computation of the Endpoint

Categories will be assigned to numeric values as follows: "Much better" = 1, "A little better" = 2, "No change" = 3, "A little worse" = 4, and "Much worse" = 5.

• Analysis of the Endpoint

The number and of percentage of subjects in each category ("Much better", "A little better", "No change", "A little worse", "Much worse") in PGI-C daily impacts will be summarized descriptively by treatment group for subjects in the FAS.

Additionally, as a key secondary efficacy analysis, the average response in PGI-C daily impacts scale, using the assigned numeric values of 1-5, will be compared between treatment groups at Day 90. An ANCOVA model, adjusting for the subject's baseline PGI-S daily impacts scale category as a quantitative covariate using the assigned numeric values of 1-5, will be used. Subjects with missing data at Day 90 will be excluded from analysis.

7.6. Pure Tone Audiometry

Standard Pure Tone Audiometry will be measured to determine a subject's threshold for hearing at various frequencies and will be performed at the Screening/Start of Lead-In, Lead-In, End of Lead-In/Treatment, Day 30, Day 60, Day 90, Day 180, and Day 270 visits. This will be performed on a calibrated audiometer by a licensed audiologist. The following frequencies will be obtained: Air: 0.25, 0.5, 1, 2, 3, 4, 6, and 8 kHz; Bone: 0.5, 1, 2, 3, and 4 kHz. If both masked and unmasked results are available for the same visit, date, ear, and frequency, the masked results will be used for analysis. Post-Screening PTA thresholds with missing response values, specifically, no response due to a subject's audiometric threshold greater than the maximum calibrated dB of the equipment at a given frequency, will be imputed using the maximum dB for the audiometry equipment plus 5 dB. The value, maximum dB for the audiometry equipment plus 5 dB, was collected on the CRF as audiometer upper limit and the result will be classified as no signal at that frequency. Missing response values at Screening will not be imputed and remain missing.

Pure tone audiometry results will be presented in a data listing for the FAS.

- 7.6.1. Air and Bone Conduction audiometry dB HL thresholds by frequency
 - Computation of the Endpoint

At each visit and by ear (left, right), the AC and BC audiometry dB HL thresholds will be recorded for each frequency (Air: 0.25, 0.5, 1, 2, 3, 4, 6, and 8 kHz; Bone: 0.5, 1, 2, 3, and 4 kHz). Left and right ears will be mapped to treated and untreated for analysis. Missing values will be imputed per Section 7.6.

• Analysis of the Endpoint

Separately for AC and BC, the hearing threshold at each frequency will be summarized descriptively for treated and untreated ears separately by visit and treatment group for subjects in the FAS.

A line plot of the mean AC audiometry thresholds by frequency will be prepared for treated and untreated ears for each treatment group with lines connecting each point.

7.6.2. Mean overall PTA (AC over 0.5, 1, 2, and 4 kHz) and BCA (BC over 0.5, 1, 2 and 4 kHz)

• Computation of the Endpoint

At each visit and by ear (left, right), the mean overall PTA will be derived by averaging the AC audiometry dB HL thresholds over 0.5, 1, 2, and 4 kHz frequencies. Left and right ears will be mapped to treated and untreated for analysis. Missing values will be imputed per Section 7.6. The BCA will be derived using the same approach. If hearing thresholds are missing for any of the 0.5, 1, 2, and 4 kHz frequencies (after imputation of records with classification of "NR"), PTA or BCA will be missing, respectively.

• Analysis of the Endpoint

The mean overall PTA will be summarized descriptively for treated ears by visit and treatment group for subjects in the FAS. The summary will be repeated for BCA.

- 7.6.3. AC and BC improvement ≥10 and ≥15 dB HL from baseline, separately, for two contiguous frequencies
 - Computation of the Endpoint

AC improvement ≥10 dB HL from baseline for two contiguous frequencies at each postbaseline visit for treated ears will be computed as 1 if the post-baseline threshold – baseline threshold is ≥10 dB HL for two contiguous frequencies and as 0, otherwise. The endpoint will utilize imputed values per Section 7.6. The AC improvement ≥15 dB HL, BC improvement ≥10 dB HL, and BC improvement ≥15 dB HL will be derived using the same approach.

• Analysis of the Endpoint

The incidence of AC improvement ≥10 dB HL from baseline for two contiguous frequencies at each post-baseline visit for treated ears will be summarized using frequencies and percentages by visit and treatment group for subjects in the FAS. The summary will be repeated for ≥15 dB HL and for BC improvement, ≥10 and ≥15 dB HL.

- 7.6.4. AC and BC improvement ≥15 and ≥20 dB HL from baseline, separately, for any frequency
 - Computation of the Endpoint

AC improvement \geq 15 dB HL from baseline for any frequency at each post-baseline visit for treated ears will be computed as 1 if the post-baseline threshold – baseline threshold is \geq 15 dB HL for any frequency and as 0, otherwise. The endpoint will utilize imputed values per Section 7.6. The AC improvement \geq 20 dB HL, BC improvement \geq 15 dB HL, and BC improvement \geq 20 dB HL will be derived using the same approach.

• Analysis of the Endpoint

The incidence of AC improvement \geq 15 dB HL from baseline for any frequency at each postbaseline visit for treated ears will be summarized using frequencies and percentages by visit and treatment group for subjects in the FAS. The summary will be repeated for \geq 20 dB HL and for BC improvement, \geq 15 dB HL and \geq 20 dB HL.

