7.4.3. Improvement ≥10% (7 words) from baseline in percentage of recognized words overall

• Computation of the Endpoint

Improvement $\geq 10\%$ from baseline in percentage of recognized words overall at each postbaseline visit for treated ears will be computed as 1 if the change from baseline in percentage of recognized words overall $\geq 10\%$ and as 0, otherwise where the change is not missing. Missing data will not be imputed. Improvement $\geq 10\%$ (7 words) from baseline in percentage of recognized words will not be computed for each signal-to-noise ratio.

• Analysis of the Endpoint

The incidence of improvement ≥10% from baseline in percentage of recognized words overall at each post-baseline visit for treated ears will be summarized using frequencies and percentages by visit and treatment group for subjects in the FAS.

In treated ears only for subjects in the FAS, post-baseline treatment group comparisons for incidence of improvement ≥10% from baseline in percentage of recognized words overall will be analyzed using a GEE model. With the binomial distribution assumption and logit link, the model will include fixed effects of treatment group, visit, interaction between visit and treatment group, baseline WIN score, interaction between baseline WIN score and visit, and randomization stratification factors. If the model fails to converge, the randomization stratification factors will be excluded from the model. The odds ratios along with 95% CIs and p-values between treatment groups will be reported by visit.

- 7.4.4. Spearman-Kärber estimates of dB thresholds for word recognition (25th, 50th (median) and 75th percentiles)
 - Computation of the Endpoint

The Spearman-Kärber estimates (25th, 50th (median) and 75th percentiles) of dB thresholds for word recognition (Wilson et al., 1973) at each visit for treated ears will be computed as

$$dB = i + (p_c * d) - (d * w)/c$$

where "p_c" is the percentile of interest, "i" is the initial dB presentation level (fixed at 24), "d" is the attenuation dB step size (fixed at 4), "c" is the number of words per decrement (fixed at 10), and "w" is the frequency of words recognized overall at each visit. Missing data will not be imputed.

• Analysis of the Endpoint

Spearman-Kärber estimates (25th, 50th (median) and 75th percentiles) will be summarized descriptively for treated ears by visit and treatment group for subjects in the FAS.

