7.4.6. Improvement ≥3 dB shifts in median Spearman-Kärber estimates from baseline

• Computation of the Endpoint

Improvement \geq 3 dB shifts in median Spearman-Kärber estimates at each post-baseline visit for treated ears will be computed as 1 if the post-baseline Spearman-Kärber estimate – baseline Spearman-Kärber estimate is \geq 3 and as 0, otherwise where the baseline and postbaseline Spearman-Kärber estimates are not missing. Missing data will not be imputed.

• Analysis of the Endpoint

The incidence of improvement ≥3 dB shifts in median Spearman-Kärber estimates at each post-baseline visit for treated ears will be summarized using frequencies and percentages by visit and treatment group for subjects in the FAS.

Post-baseline treatment group comparisons will be performed using the GEE model described in Section 7.4.3 for subjects in the FAS.

Version Date: 2	2023-01-19
-----------------	------------

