7.7. Extended High Frequency Audiometry

Extended high frequency audiometry will be performed to determine a subject's threshold for hearing at frequencies beyond those in standard pure tone audiometry at the Screening/Start of Lead-In, Lead-In, End of Lead-In/Treatment, Day 30, Day 60, Day 90, Day 180, and Day 270 visits. This will be performed on a calibrated audiometer by a licensed audiologist. The following frequencies will be obtained: Air: 9, 10, 11.2, 12.4, 14, and 16 kHz. Because some audiometers use center frequencies that vary by small amounts, sites should use the threshold at the closest listed center frequency (e.g., 11 kHz may be used for 11.2 kHz; 12.5 kHz may be used for 12.4 kHz). If both masked and unmasked results are available for the same visit, date, ear, and frequency, the masked results will be used for analysis.

Post-Screening PTA thresholds with missing response values, specifically, no response due to a subject's audiometric threshold greater than the maximum calibrated dB of the equipment at a given frequency, will be imputed using the maximum dB for the audiometry equipment plus 5 dB. The value, maximum dB for the audiometry equipment plus 5 dB. The value, maximum dB for the result will be classified as no signal at that frequency. Missing response values at Screening will not be imputed and remain missing.

Extended high frequency audiometry results will be presented in a data listing for subjects in the FAS.

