7.7.2. Mean dB HL threshold (AC over 9-16 kHz)

• Computation of the Endpoint

At each visit and by ear (left, right), the mean dB HL threshold will be derived by averaging the AC audiometry dB HL thresholds over 9-16 kHz frequencies. Left and right ears will be mapped to treated and untreated for analysis. Missing values will be imputed per Section 7.7.

• Analysis of the Endpoint

The mean dB HL threshold will be summarized descriptively for treated ears by visit and treatment group for subjects in the FAS.

7.7.3. AC improvement ≥10 dB HL and ≥15 dB HL from baseline, separately, for two contiguous frequencies

• Computation of the Endpoint

AC improvement ≥10 dB HL from baseline for two contiguous frequencies at each postbaseline visit for treated ears will be computed as 1 if the post-baseline threshold – baseline threshold is ≥10 dB HL for two contiguous frequencies and as 0, otherwise. The endpoint will utilize imputed values per Section 7.7. The AC improvement ≥15 dB HL will be derived using the same approach.

• Analysis of the Endpoint

AC improvement ≥10 dB HL from baseline for two contiguous frequencies will be summarized using frequencies and percentages for treated ears by visit and treatment group for subjects in the FAS. The summary will be repeated for AC improvement ≥15 dB HL.

7.7.4. AC improvement ≥15 and ≥20 dB HL from baseline, separately, for any frequency

• Computation of the Endpoint

AC improvement \geq 15 dB HL from baseline for any frequency at each post-baseline visit for treated ears will be computed as 1 if the post-baseline threshold – baseline threshold is \geq 15 dB HL for any frequency and as 0, otherwise. The endpoint will utilize imputed values per Section 7.7. The AC improvement \geq 20 dB HL will be derived using the same approach.

• Analysis of the Endpoint

AC improvement ≥15 dB HL from baseline for any frequency will be summarized using frequencies and percentages for treated ears by visit and treatment group for subjects in the FAS. The summary will be repeated for AC improvement ≥20 dB HL.

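### Five SAP responder rules (7.4.6, 7.6.3, 7.6.4, 7.7.3, 7.7.4) subtract in the wrong order and, as written, count worsened ears as improved

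*SAP*

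**What the plan says.** Each of the five sections is titled as an improvement endpoint and gives an explicit computation.

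- **SAP 7.6.3** (standard audiometry, two contiguous frequencies): air-conduction improvement is "computed as 1 if the post-baseline threshold – baseline threshold is ≥10 dB HL for two contiguous frequencies and as 0, otherwise". The 15 dB cut-off and bone conduction follow the same approach.
- **SAP 7.6.4** (any single frequency): "computed as 1 if the post-baseline threshold – baseline threshold is" at or above 15 dB HL, with 20 dB and bone conduction handled likewise.
- **SAP 7.7.3 and 7.7.4** (extended high frequency): the first is "computed as 1 if the post-baseline threshold – baseline threshold is ≥10 dB HL for two contiguous frequencies", also at 15 dB. The second applies the same subtraction to any frequency at 15 and 20 dB.
- **SAP 7.4.6** (WIN): "computed as 1 if the post-baseline Spearman-Kärber estimate – baseline Spearman-Kärber estimate is" at or above 3 dB.

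On use, 7.4.6 states: "Post-baseline treatment group comparisons will be performed using the GEE model described in Section 7.4.3 for subjects in the FAS". The model in 7.4.3 reports odds ratios, confidence intervals and p-values by visit. Sections 7.6.5 and 7.7.5 build composite responders from the audiometric flags and tabulate them. Their text makes the GEE on the composites optional, while Table 7-2 lists it without qualification.

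**The concern.** A hearing threshold is the level a subject needs in order to hear, so improvement is a fall. A rule that requires post-baseline minus baseline to exceed a positive number selects ears whose threshold has risen.

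Programmed literally, these tables would report deterioration under an improvement heading for supplementary responder summaries of two protocol secondary endpoints, WIN and audiometry. In the 7.4.6 GEE, an odds ratio above 1 for FX-322 over placebo would mean more worsening on FX-322. The rules would also collide with the protocol's adverse events of special interest (Section 14), which include a loss of at least 20 dB at one frequency or at least 10 dB at two adjacent frequencies. The same ear could be tabulated both as improved and as such an event. That overlap is not exact, because the safety criterion requires an asymmetric loss and compares with Visit 3.

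**Working it through.** The plan gives no figure to reproduce here; the question is the sign of a derivation rule.

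**Step 1: direction of the audiometric scale.** SAP 7.6 describes no response as an "audiometric threshold greater than the maximum calibrated dB of the equipment at a given frequency". SAP 7.7 says such a value "will be imputed using the maximum dB for the audiometry equipment plus 5 dB". The worst outcome therefore takes the highest number, and higher dB HL is worse.

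**Step 2: direction of the WIN scale.** SAP 7.4.4 fixes the start level at 24 dB, the step at 4 dB and the words per step at 10. For the median (percentile 0.5) and w words recognized out of 70:

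dB = 24 + 0.5 × 4 − 4w/10 = 26 − 0.4w

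More words give a lower dB, at 0.4 dB per word. The 3 dB cut-off equals 3/0.4 = 7.5 words.

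**Step 3: audiometric rules applied to illustrative ears.** The 7.6.4 rule at 15 dB, with one frequency changing. SAP Section 3 averages Lead-in and Day 1 for efficacy endpoints and takes the last pre-dose value for other analyses. Table 7-2 leaves its efficacy mark off both audiometry blocks, so both baselines are shown.

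| Lead-in / Day 1 / post (dB HL) | Post − averaged baseline | Post − last value | True direction | Flag as written |
|---|---|---|---|---|
| 60 / 55 / 40 | 40 − 57.5 = −17.5 | 40 − 55 = −15 | better | 0 |
| 40 / 45 / 60 | 60 − 42.5 = +17.5 | 60 − 45 = +15 | worse | 1 |
| 60 / 60 / 40 | −20 | −20 | better | 0 |
| 40 / 40 / 60 | +20 | +20 | worse | 1 |

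The reversal does not depend on the choice of baseline. When two contiguous frequencies both change by 20 dB, all four cut-offs (two contiguous at 10 and 15, any at 15 and 20) flag the worsened ear and miss the improved one. Reversing the subtraction corrects all of these.

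**Step 4: WIN rule set against 7.4.3.** SAP 7.4.3 works from the same word counts in the right direction: "computed as 1 if the change from baseline in percentage of recognized words overall" is at least 10%, which is 7 of 70 words.

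| Words, baseline to post | Median dB | Change in dB | 7.4.6 as written | Change in % words | 7.4.3 |
|---|---|---|---|---|---|
| 30 to 38 | 14.0 to 10.8 | −3.2 | 0 | 8/70 = +11.4 | 1 |
| 38 to 30 | 10.8 to 14.0 | +3.2 | 1 | −11.4 | 0 |

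**Step 5: is the conflict general?** The WIN baseline is a two-visit average and can be a half word. That gives 141 possible baselines and 71 possible post-baseline counts: 141 × 71 = 10,011 pairs.

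- 7.4.6 as written flags 4,032 pairs, and 7.4.3 flags none of them.
- With the sign reversed, 7.4.6 flags 4,032 pairs, and 7.4.3 flags all of them.
- 7.4.3 flags 4,096 in total. The other 4,096 − 4,032 = 64 are gains of exactly 7 words (2.8 dB), which fall between the two cut-offs.

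These counts show that the two rules can never agree on a responder as written. They are not expected frequencies in the trial.

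**Step 6: how far the reversal goes.** It is not a full mirror image. Ears with small changes score 0 under either sign, and an ear with +15 dB at one frequency and −15 dB at another scores 1 in 7.6.4 under either.

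**The case against.** The best defence is that nobody would be misled. Every rule is titled as an improvement, so a competent programmer would see the intended direction. Table specifications are held in separate documents (SAP Section 1), so no wrong output has been shown. The four single-criterion audiometric tables are descriptive, and the composite GEEs are optional in the text. The key secondary WIN endpoint is the change in percentage of words, which is correct. The threshold, mean and change summaries elsewhere in 7.6 and 7.7 are also correct and would expose a reversed responder table.

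All of this stands, and it limits the severity. It does not remove the error. The computation paragraph is the derivation rule, the same reversal appears in five sections, and nothing in either document corrects it. The 7.4.6 GEE is a firm commitment rather than an option.

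It is also fair to say that the mismatch over optional GEEs and the misdirected cross-reference in 7.6.5 are separate, clerical matters. They are worth tidying in the same edit but carry no weight in the finding.

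**Conclusion.** The concern holds. The rules in SAP 7.4.6, 7.6.3, 7.6.4, 7.7.3 and 7.7.4 are wrong as written: followed literally, they score changes for the worse at or beyond the cut-off as improvement and score equal changes for the better as 0. The composites in 7.6.5 and 7.7.5 inherit this. The conclusion rests only on the SAP's own definitions of the two scales. The example thresholds are illustrative.

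The reach is limited. The primary responder analysis, the key secondary WIN and PGI-C analyses, the fixed test sequence (7.1.4), the plain change scores in 7.4.5 and 7.6.6, and the no-signal shift tables (7.7.6 to 7.7.8) are unaffected. This should be fixed before the outputs are produced, but it does not threaten the trial's main conclusion.

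**What to change.** - In 7.6.3, 7.6.4, 7.7.3 and 7.7.4, define improvement as baseline minus post-baseline threshold of at least 10, 15 or 20 dB HL, as applicable.
- In 7.4.6, define it as baseline minus post-baseline median Spearman-Kärber estimate of at least 3 dB.
- Carry the corrected flags through the composites in 7.6.5 and 7.7.5.
- Leave the change scores in 7.4.5 and 7.6.6 alone; post-baseline minus baseline is right there.
- Check the programs in both directions. An ear going from 60 to 40 dB HL at two contiguous frequencies, with the rest unchanged, and a WIN gain from 30 to 38 words must score 1. The mirror cases (40 to 60 dB HL, 38 to 30 words) must score 0. Improving cases alone are not enough, because a program using the absolute difference would pass them.
- In the same edit, point 7.6.5 to Section 7.6.3 instead of 7.6.2 for the two-contiguous-frequency rule, and make the text of 7.6.5 and 7.7.5 agree with Table 7-2 on whether the composite GEEs will be run.

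The cost is SAP wording and a check of the program specifications. No new data are needed, and the primary and key secondary analyses do not change.

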7.6.5. AC and BC composite improvement from baseline

• Computation of the Endpoint

The first AC composite improvement endpoint is defined as the occurrence of either or both of the following conditions for a given subject's ear for a given visit: 1) AC improvement ≥ 10 dB HL from baseline for two contiguous frequencies as described in Section 7.6.2 or 2) AC improvement ≥ 15 dB HL from baseline for any frequency as defined in Section 7.6.4. The first BC composite improvement endpoint is defined using the same approach.

The second AC composite improvement endpoint is defined as the occurrence of either or both of the following conditions for a given subject's ear for a given visit: 1) AC

Page 36 of 64

Version Date: 2023-01-19	Version: 2.0

improvement ≥15 dB HL from baseline for two contiguous frequencies as described in Section 7.6.2 or 2) AC improvement ≥20 dB HL from baseline for any frequency as defined in Section 7.6.4. The second BC composite improvement endpoint is defined using the same approach.

• Analysis of the Endpoint

The incidence of each AC composite improvement endpoint at each post-baseline visit for treated ears will be summarized using frequencies and percentages by visit and treatment group for subjects in the FAS. The summary will be repeated for each BC composite improvement endpoints.

In treated ears only for subjects in the FAS, post-baseline treatment group comparisons through day 90 for the incidence of AC composite improvement from baseline may be analyzed using a GEE model. With the binomial distribution assumption and logit link, the model will include fixed effects of treatment group, visit, interaction between visit and treatment group, baseline mean overall PTA, interaction between baseline mean overall PTA and visit, and randomization stratification factors. If the model fails to converge, the randomization stratification factors will be excluded from the model. The odds ratios along with 95% CIs and p-values between treatment groups will be reported by post-baseline visit. The analysis may be repeated for the incidence of BC composite improvement using a similar approach replacing the baseline mean overall PTA with the baseline mean overall BCA.

7.6.6. Change from baseline in Mean overall PTA and BCA

• Computation of the Endpoint

Using the mean overall PTA from Section 7.6.2, change from baseline in PTA will be computed as w - b where "w" is the post-baseline PTA and "b" is the PTA at baseline for each visit by ear (left, right). Left and right ears will be mapped to treated and untreated for analysis. The change from baseline in BCA will be derived using the same approach.

• Analysis of the Endpoint

The change from baseline in mean overall PTA will be summarized descriptively for treated ears by visit and treatment group for subjects in the FAS. The summary will be repeated for BCA.

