**Statistical Analysis:**

**Sample Size:** The sample size of 112 evaluable subjects, in a 1:1 allocation ratio of FX-322 and Placebo provides 80% to show improvements in WR.

**Statistical Methods:** Descriptive summaries will be provided for patient disposition, demographic and baseline disease data by treatment group.

Efficacy analysis of continuous endpoints will be examined via a Mixed Model for Repeated Measures (MMRM). Inferential analyses for categorical endpoints will be analysed using univariate methods and/or Generalized Estimating Equations (GEEs) (or appropriate longitudinal methods as detailed in the SAP). When appropriate, models will include adjustments for baseline as well as the stratification factors used at randomization and clinically relevant confounders as identified in the SAP. Departures of these models from the statistical assumptions will be assessed and alternative approaches may be employed.

Summary statistics for efficacy endpoints will be provided by treatment group over the study and at specific timepoints. Comparisons between FX-322 and placebo and 95% confidence interval of the difference will also be calculated.

The incidence of treatment-emergent adverse events will be presented by preferred term and body system using the Medical Dictionary for Regulatory Activities (MedDRA®). Tabulations will be provided by seriousness, severity, and relationship to study drug. Audiology, tympanometry and otologic data will be presented as summary statistics at each timepoint as well as changes from baseline and/or shift tables. All subjects exposed to study drug will be included in the Safety Analysis Set and included in the safety analyses according to the actual treatment group regardless of the randomized assignment.

Details of all planned statistical analyses and methods will be provided in the SAP, and will be finalized prior to study blind break for the primary analysis.

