### **15.5 Efficacy Analyses**

Primary efficacy analysis will be conducted after all subjects have either completed follow-up visits or early discontinued from study. Primary analysis will be performed in an unblinded fashion for analysis purpose while subjects not completing observation visits will continue to be followed as being blinded to treatment assignment.

Efficacy endpoints will be summarized descriptively at each study timepoint. Calculations will include the observed data at each timepoint, and if relevant, the change from baseline (baseline defined as the average across the pre-treatment timepoints).

For continuous endpoints means, medians, standard deviations, minimums and maximum will be provided. For categorical endpoints the number and percent of subjects within each category will be calculated. For descriptive analyses, subjects with missing data will be excluded for a particular calculation.

Inferential statistical methods examining continuous endpoints will be examined via a Mixed Model for Repeated Measures (MMRM). Inferential analyses for categorical endpoints will be analysed using univariate methods and/or Generalized Estimating Equations (GEEs) (or appropriate longitudinal methods as detailed in the SAP). When appropriate, models will include adjustments for baseline as well as the stratification factors used at randomization and clinically relevant confounders as identified in the SAP. Departures of these models from the statistical assumptions will be assessed and alternative approaches may be employed.

Efficacy endpoints will be analysed using the FAS, and complete details of these analyses will be included in the SAP.

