7.1.5. Model Fitting

Inferential statistical methods examining continuous endpoints will be examined via a Mixed-effects Model for Repeated Measures (MMRM). Inferential analyses for categorical endpoints will be analyzed using univariate methods and/or Generalized Estimating Equations (GEE). The MMRM and GEE analyses will employ an unstructured working correlation matrix.

Further details for each of the planned models and analyses are provided in subsequent sections.

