9.2.1. Mean total score, individual subscale scores, and loudness score

• Computation of the Endpoint

At each visit, the mean total TFI score and individual subscale scores will be computed per Section 14.3. The loudness score will be the response from item 2.

• Analysis of the Endpoint

The mean total TFI score, individual subscale scores, and loudness score will be summarized descriptively by visit and treatment group for subjects in the FAS.

9.2.2. Change from baseline in mean total score, individual subscale scores, and loudness score

• Computation of the Endpoint

The change from baseline to each post-baseline visit will be computed as w - b where "w" is the post-baseline score and "b" is the score at baseline.

• Analysis of the Endpoint

The change from baseline to each post-baseline visit in mean total TFI score, individual subscale scores, and loudness score will be summarized descriptively by visit and treatment group for subjects in the FAS.

9.3.	Research Assessment on	Quality of Life
	is a PRO questionnaire	
		The subject will complete

the instrument at the End of Lead-In/Treatment and Day 90 visits.

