11. CHANGES TO THE ANALYSES PLANNED IN THE PROTOCOL

Not applicable.

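### The SAP plans no between-arm estimate for TFI or the continuous audiometric outcomes and is inconsistent on the composite model, although the protocol synopsis promises treatment differences with 95% CIs

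*SAP*

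**What the plan says.** Protocol 2 and 9 list standard pure-tone audiometry, extended-high-frequency audiometry and TFI as secondary endpoints, and protocol 13.1 describes them as efficacy measurements. The synopsis assigns continuous efficacy endpoints to an MMRM and adds: "Comparisons between FX-322 and placebo and 95% confidence interval of the difference will also be calculated". Protocol 15.5 and SAP 7.1.5 both name the MMRM as the inferential method for continuous endpoints.

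The SAP endpoint sections read differently:

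- 7.6.6, PTA and bone conduction average (BCA): "The change from baseline in mean overall PTA will be summarized descriptively for treated ears by visit and treatment group for subjects in the FAS". BCA is handled identically.
- 7.6.8 and 7.6.9, low- and high-frequency air-conduction means: descriptive by visit and arm.
- 7.7.2, the 9-16 kHz mean: "The mean dB HL threshold will be summarized descriptively for treated ears by visit and treatment group for subjects in the FAS".
- 9.2.2, TFI: "The change from baseline to each post-baseline visit in mean total TFI score, individual subscale scores, and loudness score will be summarized descriptively".
- 7.6.5 and 7.7.5, composite improvement: treatment comparisons through Day 90 "may be analyzed using a GEE model", with odds ratios, 95% CIs and p-values by visit. Table 7-2 lists the GEE for both composites with no such qualifier.

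SAP 11, on changes from the protocol's analyses, reads "Not applicable".

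**The concern.** Pure-tone thresholds help show whether a gain in word recognition is a gain in audibility, so the between-arm difference in dB is what a reader will look for beside the primary result. Followed as written, the SAP produces no such difference, no interval and no baseline adjustment for the continuous thresholds or for TFI. The one comparative audiometric analysis is a GEE on dichotomized composites, and text and table disagree on whether it will be run. Anyone reading the protocol would expect more, and SAP 11 does not say that the plan was narrowed.

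**Working it through.** **Step 1: what is planned, outcome by outcome.**

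| Outcome | SAP section | Change from baseline defined? | Between-arm estimate planned? |
|---|---|---|---|
| Mean PTA and BCA | 7.6.2, 7.6.6 | Yes | No |
| Low air-conduction mean (0.25-2 kHz) | 7.6.8 | No | No |
| High air-conduction mean (3-8 kHz) | 7.6.9 | No | No |
| 9-16 kHz mean | 7.7.2 | No | No |
| TFI total, subscales, loudness | 9.2.1, 9.2.2 | Yes | No |
| Pure-tone composites | 7.6.5 | Responder | GEE odds ratio: optional in text, unqualified in Table 7-2 |
| Extended-high-frequency composite | 7.7.5 | Responder | GEE odds ratio: optional in text, unqualified in Table 7-2 |

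**Step 2: can the composite GEE stand in for the missing estimates?** Not as written. SAP 7.6.3, 7.6.4, 7.7.3 and 7.7.4 score improvement when post-baseline minus baseline threshold reaches the cut-off. SAP 7.6 and 7.7 set a no-response to equipment maximum plus 5 dB, so a higher threshold is worse hearing. A fall of 10 dB at two contiguous frequencies gives -10 and meets no 10 dB criterion; a rise of 10 dB gives +10 and scores 1. Read literally, the GEE would estimate the odds of worsening.

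**Step 3: arm sizes.** The plan states no precision figure for these outcomes. SAP 2.2.2 gives 62 per arm, and SAP 2.5 gives 112 evaluable, so 56 per arm. The stated 124 is close to 112/0.9 = 124.4 and 112 x 1.1 = 123.2.

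**Step 4: precision of an added unadjusted difference.** Half-width = t(0.975, 2n-2) x SD x sqrt(2/n), which is 0.375 SD at 56 per arm and 0.356 SD at 62. The documents give no SD. For assumed SDs of 5, 7.5, 10, 15 and 20 units, the half-width at 56 per arm is 1.9, 2.8, 3.7, 5.6 and 7.5.

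**Step 5: what baseline adjustment adds (illustration).** Assume PTA spread evenly over the eligible 35-85 dB (protocol 10.5.2), equal variance at follow-up, 62 per arm, and baseline-to-follow-up correlation r.

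- SD = 50/sqrt(12) = 14.43 dB. SE of a raw mean difference = 14.43 x sqrt(2/62) = 2.59, half-width 1.96 x 2.59 = 5.1 dB.
- Change score: half-width = 1.96 x 2.59 x sqrt(2(1-r)).
- ANCOVA: half-width = 1.96 x 2.59 x sqrt(1-r^2).

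| r | Raw visit mean | Change score | ANCOVA |
|---|---|---|---|
| 0.85 | 5.1 | 2.8 | 2.7 |
| 0.90 | 5.1 | 2.3 | 2.2 |
| 0.95 | 5.1 | 1.6 | 1.6 |

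SAP 7.6.6 already tabulates change, so for PTA the relevant comparison is the last two columns: a gain of about 0.1 dB at most. The raw-mean column applies only to the type of table planned in 7.6.8, 7.6.9 and 7.7.2. Even there it shows direction, not size, because the 35-85 dB range is for the 0.5, 1, 2 and 4 kHz average and not for the low, high or 9-16 kHz means.

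**The case against.** The other side has real points.

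- **The protocol is not of one voice.** The synopsis's safety paragraph plans audiology data as summary statistics with changes from baseline or shift tables, and protocol 15.6 lists questionnaire responses among the descriptive summaries. The 95% CI sentence is in the synopsis and not in 15.5. The MMRM statements in 15.5 and SAP 7.1.5 can be read as naming the model where inference is done, not as requiring inference everywhere, and the protocol leaves details to the SAP. This softens the conflict. It does not remove it: the synopsis applies the MMRM to continuous efficacy endpoints without that limit, and protocol 13.1 places these measures under efficacy.
- **The endpoints carry no alpha.** They lie outside the fixed sequence in SAP 7.1.4. Table 7-2 does not mark audiometry as efficacy, and TFI sits under Other Analyses. That limits the consequence, but a nominal difference with an interval needs no alpha.
- **A crude difference can be derived** from the n, mean and SD required by SAP 3. This stands; what is missing is a prespecified, adjusted one.

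A reader might infer three stronger things that the documents do not support. First, that there is no effect estimate for audiometry at all: SAP 7.6.5 and 7.7.5 specify a baseline-adjusted GEE with odds ratios and CIs, and Table 7-2 lists it. Second, that the choice to run it will be made after unblinding: nothing says when the optional wording is resolved, and table specifications are in separate documents. Third, that about 5 dB of uncertainty attaches to PTA change: that figure belongs to raw visit means under an assumed spread.

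**Conclusion.** The point holds in a limited form. TFI and the continuous pure-tone and extended-high-frequency outcomes have no planned between-arm estimate or CI. This is in tension with the protocol synopsis and is not declared in SAP 11. The composite GEE is specified, but it is inconsistent between text and table and cannot serve as an estimate of benefit until the improvement sign is corrected. The primary test and the fixed sequence are unaffected.

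For PTA and TFI change, the loss is a prespecified, baseline-adjusted difference, with little loss of precision. Only the low, high and 9-16 kHz means are likely to gain materially in precision, by an amount that depends on SDs and correlations the documents do not state.

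**What to change.** 1. In SAP 7.6.6, 7.6.8, 7.6.9 and 7.7.2, analyse change from baseline through Day 90 with the MMRM of 7.4.2 (treatment, visit, their interaction, the outcome's own baseline, baseline by visit, strata). Report the Day 90 LS mean difference with a nominal 95% CI. State which baseline rule in SAP 3 applies, since Table 7-2 does not mark audiometry as efficacy. For 9-16 kHz, note that no-response values are set to equipment maximum plus 5 dB, and read the result alongside the no-signal shift tables (7.7.6 to 7.7.8).
2. In 9.2.2, add a Day 90 ANCOVA of TFI change on baseline TFI and the randomization strata. Through Day 90, TFI has only one scheduled post-baseline assessment.
3. In 7.6.3, 7.6.4, 7.7.3 and 7.7.4, define improvement as baseline minus post-baseline. Only then change *may* to *will* in 7.6.5 and 7.7.5, to match Table 7-2.
4. Label all of these as nominal and outside the fixed sequence.

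If the sponsor prefers descriptive tables, the minimum is to declare the departure in SAP 11 and reconcile 7.6.5 and 7.7.5 with Table 7-2; the sign still needs correcting.

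The cost is SAP wording and a few models on data already collected, largely reusing a model the SAP already specifies. The downside is a few more intervals unadjusted for multiplicity.
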